10.1.1. Study Visits

The study will consist of a Screening visit on Day -2 (± 1), Baseline visit on Day 1 (if applicable, the Screening and Baseline visits can both be done on Day 1), Phone contacts on Days 3, 5 and 7 (± 1), a TOC visit 14 (± 3) days after Baseline, FU visits at: 14 (± 3) days after EOT, 30 (± 4) after Baseline, 30 (± 4) after EOT and 60 (± 4) days after EOT.

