12. STUDY TREATMENTS

12.1. Study Treatment Groups

Treatment Cycle 1 – ALL randomized subjects:

Subjects who meet all the inclusion and none of the exclusion criteria will be randomized to treatment and stratified by group based on the *Candida* species and presence or absence of underlying conditions. Subjects will receive open-label oral ibrexafungerp 300 mg BID for one, three or seven consecutive days per the table below:

Ibrexafungerp Treatment Groups:

Treatment Group	Criteria	*Ibrexafungerp Dose (300mg AM and 300mg PM) Randomization and Stratification
Group A	Subjects without underlying medical conditions AND known to have isolates other than C glabrata , C krusei , C auris	1 Day dosing N=50
Group B	Subjects with underlying medical conditions: DM, immunocompromised conditions (e.g. HIV), debilitation, immunosuppressive therapy (e.g. corticosteroids), recurrent VVC (≥ 3 episodes/year) AND/OR known to have C glabrata , C krusei or C auris isolates	3 Days OR 7 Days dosing Randomized 1:1 N=50:50

*Days of treatment is per CDC Guidelines (<https://www.cdc.gov/std/treatment-guidelines/candidiasis.htm>)

Enrollment will continue until the target number in each cohort is reached.

Treatment Cycle 2: A second treatment cycle will be allowed for subjects who did not achieve sufficient clinical improvement (e.g. VSS remains ≥ 3) on the randomized treatment (Cycle 1) as evaluated at the TOC and FU visits. A second treatment cycle will also be allowed for subjects with clinical cure/improvement/success who experience a recurrence before the last FU visit. During Cycle 2, subjects may receive additional treatment with ibrexafungerp for a period up to 14 days as recommended by the investigator and following discussion with the sponsor.

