15. STUDY SCHEDULE

Detailed schedules of all study visits and procedures are presented in Schedule of Visits and Procedures ([Table 1](#)).

The actual visits will be dependent on the Dosing Group i.e there may be overlapping visits.

Subjects entering Treatment Cycle 2, will follow the same Schedule of Visits and Procedures, starting with Baseline visit and may have visits that are Not Applicable during Treatment Cycle 1.

Table 1: Schedule of Visits and Procedures (Study SCY-078-307b)

Visit	V1 Screening ^a	V2 Baseline ^a	At Home	V3 TOC	V4 FU	V5 FU	V6 FU	V7 FU	Unscheduled Visits ^b
Day (allowable window)	Day -2(±1)	Day 1	Days 2-7	14 ±3 days post Baseline	14 ±3 days post EOT	30±4 days post Baseline	30 ±4 days post EOT	60 ±4 days post EOT	
Study Procedures									
Informed consent	X								
Enrollment and assignment of Subject ID number	X								
Inclusion/exclusion criteria ^c	X	X							
Medical history and demographics	X								
Abbreviated physical exam	X			X					If needed
Vital Signs ^k	X	X		X					If needed
Urine pregnancy test ^c	X			X					If needed
Safety laboratory blood tests ^d	X			X					If needed

Visit	V1 Screening ^a	V2 Baseline ^a	At Home	V3 TOC	V4 FU	V5 FU	V6 FU	V7 FU	Unscheduled Visits ^b
Day (allowable window)	Day -2(±1)	Day 1	Days 2-7	14 ±3 days post Baseline	14 ±3 days post EOT	30±4 days post Baseline	30 ±4 days post EOT	60 ±4 days post EOT	
Rating of vulvovaginal symptoms by the Subject^e	X	X	X	X	X	X	X	X	If needed
Vaginal Examination and rating of vulvovaginal signs by the Investigator^e	X			X	X	If symptoms	If symptoms	If symptoms	If needed
Vulvovaginal sample for other pathogens^e	X			If needed	If needed	if needed	If needed	If needed	If needed
Vulvovaginal sample for KOH and pH^e	X			If symptoms	If symptoms	If symptoms	If symptoms	If symptoms	If needed
Vulvovaginal sample for fungal culture^e	X			X	X	If symptoms	If symptoms	If Symptoms	If needed
Quality of Life Questionnaire		X		X	X	X	X	X	
Study drug dosing		X	X						
Study drug container(s) collection and subject data reviewed				X					
Phone Contact^h			X						
Prior and concomitant medication reviewⁱ	X	X	X	X	X	X	X	X	X
AE monitoring^j	X-----X				X	X	X	X	X

Abbreviations: AE = adverse event; D = day; TOC = test of cure; V = visit; FU = follow up

- a) Screening and Baseline may occur on the same day.
- b) Unscheduled visits can occur if the investigator determines there is a need for one outside of the scheduled per protocol visits.

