16.9. Adverse Event Collection Timeframe

AEs will be recorded and reviewed at all scheduled and unscheduled study visits from the time the ICF is signed through TOC visit. New AEs starting after TOC will be recorded only if they led to the use of other antifungal medications or topical vaginal treatment, if they are a vaginal bacterial or parasitic infection, or if they are deemed related to the previously administered study drug.

All AEs reported by the subject or observed by members of the clinical staff will be evaluated by the principal investigator (PI) or qualified designee. The PI will attempt, if possible, to establish a

diagnosis based on presenting signs and symptoms. The nature of the AE, time of onset relative to study drug administration, duration, severity, and relationship to treatment should be determined. Details of any corrective treatment must be recorded in the eCRF. The PI will determine whether any changes have occurred in baseline signs and symptoms. All AEs and SAEs will be collected in the eCRF.

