6.5.1. Efficacy Analysis (Treatment Cycle 2)

The proportion of Cycle 2 subjects enrolled in MITT, ITT and PP populations will be summarized in each table.

Secondary, and exploratory efficacy analysis will be analyzed the same as for cycle 1.

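### Full AE recording ends at a Baseline-anchored TOC, so for a 14-day Cycle 2 it stops between 2 days before and 4 days after the last dosing day

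*Protocol*

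**What the plan says.** Protocol 16.9 (repeated in 14.19) sets the period of full recording: "AEs will be recorded and reviewed at all scheduled and unscheduled study visits from the time the ICF is signed through TOC visit". From then on, "New AEs starting after TOC will be recorded only if they led to the use of other antifungal medications", or to topical vaginal treatment, if they are vaginal bacterial or parasitic infections, or "if they are deemed related to the previously administered study drug". Footnote j of Table 1 repeats the restriction. Sections 13.1 and 14.18 and footnote i narrow the recording of concomitant medications at the same visit.

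The cut-off is tied to Baseline. Section 10.1.1 specifies "a TOC visit 14 (± 3) days after Baseline" for every duration. Dosing in Cycle 1 lasts 1 day in Group A and 3 or 7 days, randomised 1:1, in Group B (section 12.1). For the second cycle the same section says: "During Cycle 2, subjects may receive additional treatment with ibrexafungerp for a period up to 14 days". Section 15 adds: "Subjects entering Treatment Cycle 2, will follow the same Schedule of Visits and Procedures, starting with Baseline visit".

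After dosing starts, safety laboratory tests and vital signs are scheduled only at TOC (14.7, 14.17, Table 1). For Cycle 2 efficacy, SAP 6.5.1 says: "Secondary, and exploratory efficacy analysis will be analyzed the same as for cycle 1". In Cycle 1 those outcomes are summarised at TOC and at the follow-up visits (SAP 6.4.2.2).

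The AE period is not stated consistently. The synopsis safety evaluation text ends it at TOC. Section 10.1.1.7 has AEs documented at every visit without the restriction, and 18.7.1 gives a start but no end. SAP 6.6.1 defines a TEAE from first dose with no closing date, and no rule assigns an event to a cycle.

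**The concern.** An AE cut-off is normally placed some fixed time after the last dose. Here it is fixed from the first dose, so each extra day of treatment removes a day of full recording after treatment. At the Cycle 2 maximum nothing may be left, and an early TOC inside its window can fall while the subject is still taking drug.

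The two earlier Phase 3 trials described in Protocol 7.1.4 used one day of dosing, so the longer courses are the safety information this trial adds in VVC patients. If full recording stops during or just after the longest course, a new non-serious, non-vaginal event that led to no antifungal or topical vaginal treatment survives only if an investigator who knows the treatment calls it related. The same visit carries the only scheduled post-dosing laboratory tests and vital signs, and its Cycle 2 clinical and mycological outcomes may be readings on treatment. No rule in the SAP marks them as such.

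**Working it through.** The documents state no length of AE follow-up after the last dose, so there is no figure to reproduce. The check is date arithmetic.

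**Inputs**

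- Baseline is Day 1, and TOC is Baseline + 14 with a window of ±3 (Protocol 10.1.1). Nominal TOC = 1 + 14 = Day 15; earliest = Day 12; latest = Day 18.
- The last dosing day is Day 1, 3 or 7 in Cycle 1, and Day 14 for the longest Cycle 2 course (12.1).
- Cycle 2 restarts the schedule at its own Baseline (15).
- V4 is 14 (±3) days after end of treatment (10.1.1, Table 1).

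**Full recording after the last dosing day = TOC day − last dosing day**

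| Course | Earliest TOC | Nominal TOC | Latest TOC |
|---|---|---|---|
| 1 day | 12 − 1 = 11 | 15 − 1 = 14 | 18 − 1 = 17 |
| 3 days | 12 − 3 = 9 | 15 − 3 = 12 | 18 − 3 = 15 |
| 7 days | 12 − 7 = 5 | 15 − 7 = 8 | 18 − 7 = 11 |
| 14 days (Cycle 2) | 12 − 14 = −2 | 15 − 14 = 1 | 18 − 14 = 4 |

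The earliest in-window TOC is Day 12, so it can precede the last dosing day for courses of 13 or 14 days.

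**Sensitivity to day counting.** If TOC is counted as study Day 14, every entry drops by 1: nominally 13, 11, 7 and 0, with −3 to +3 for the 14-day course. Section 14.15 allows an evening home start in Cycle 1, which moves the last dose one calendar day later. If the same is assumed for Cycle 2, each entry again drops by 1. With both, the 14-day course has −1 nominally (−4 to +2). The gap between the 3- and 7-day arms is 12 − 8 = 4 days under every convention.

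**Full recording from first dose = TOC day − Day 1.** This is 15 − 1 = 14 days (11 to 17) in every Cycle 1 arm.

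**Effect of moving the cut-off to V4.** V4 day = last dosing day + 14, which is Day 15, 17, 21 or 28 for 1, 3, 7 or 14 days of dosing. Full recording after the last dosing day becomes 14 days (11 to 17) for every duration. It runs past nominal TOC (Day 15) by 0, 2, 6 and 13 days. Within Group B, V4 falls 21 − 17 = 4 days later in the 7-day arm than in the 3-day arm.

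**The case against.** Several stronger readings are tempting, and the documents do not support them.

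- *The 3- versus 7-day AE comparison is biased in favour of the longer course.* Both arms have the same window from first dose, and SAP 6.6.1 counts TEAEs from first dose. Less time after the last dose does not by itself lower incidence over an equal window. What differs in Cycle 1 is only how much is seen after treatment ends.
- *AE recording stops at TOC.* It narrows. Related events, vaginal bacterial or parasitic infections, and events leading to antifungal or topical vaginal treatment are still recorded. All SAEs during the study must be reported (16.10, Appendix 3). The possible loss is confined to new, non-serious events outside those categories.
- *The earlier trials' TEAE rates show how much is lost.* The 60.7% and 33.2% in section 7.1.4 are whole-trial rates after one day of dosing, beside 50.8% and 29.1% on placebo. They do not measure events starting after TOC.
- *Cycle 2 efficacy will rest only on readings taken during treatment.* V4 has signs, symptoms and culture for everyone (10.1.1.5, Table 1), and the SAP already summarises outcomes at follow-up visits. What is missing is a rule that makes V4 the main reading and marks TOC readings taken on treatment.

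Two further objections have weight. A negative interval needs an optional second cycle at or near its maximum length and an early TOC. The Baseline anchor was also chosen deliberately: the revision history attributes it to regulator comments. That explains the efficacy visit, but does not require the AE cut-off to be tied to it. Even an on-time TOC leaves only about one day after a 14-day course.

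Finally, a cut-off at V4 makes the window from first dose differ by duration, which would raise all-cause incidence in the longer arms mechanically. That objection stands, and the fix has to deal with it.

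**Conclusion.** The point holds, chiefly for Cycle 2. Followed as written, full AE recording for a 14-day second course ends between 2 days before and 4 days after the last dosing day, nominally 1 day after. In Cycle 1, full recording after the last dosing day is shorter for longer courses (nominally 14, 12 and 8 days), but the randomised incidence comparison is not shown to be distorted.

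How many events would be missed cannot be estimated from the documents, which give neither the number of subjects expected in Cycle 2 nor the rate of events after TOC.

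The figures assume that Baseline is Day 1, and that TOC in the AE rule means each cycle's own TOC. If it meant only the Cycle 1 TOC, any Cycle 2 begun after that visit would fall wholly under restricted recording. The text does not settle this, which is a further reason to state the window for each cycle. The change should be made, but the trial's primary result does not depend on it.

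**What to change.** **Protocol.** In 14.19, 16.9 and Table 1 footnote j, record all AEs through the later of TOC and V4 in each cycle. Make the matching change for concomitant medications in 13.1, 14.18 and footnote i. Reconcile the synopsis safety text, 10.1.1.7 and 18.7.1 with the result.

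**SAP.** Define the AE window for each cycle. Keep a Cycle 1 AE table cut at TOC, so that the 3- and 7-day arms are compared over equal windows, and present the table through V4 separately. In 6.5.1, name V4 as the main Cycle 2 efficacy visit, and flag as on-treatment any Cycle 2 TOC efficacy, laboratory or vital-sign reading taken on or before the last dose.

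**Cost.** No new visit is needed, because V4 already includes AE and medication review for every subject. There is a little more data entry, and the all-cause AE window through V4 differs by duration, which the TOC-cut table handles for Cycle 1. If data collection is already complete, the SAP changes can still be made before database lock, but unrecorded events cannot be recovered. Nothing here alters a dose, a treatment duration or a rule for clinical management.

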16.10. Serious Adverse Event Reporting Requirements

All SAEs must be reported within 24 hours of the site becoming aware of the SAE ([Appendix 3](#)). Any event that is serious, study drug-related, and unexpected as assessed by the medical monitor or the Sponsor will be submitted to the regulatory authorities in accordance with national regulatory laws and regulations. The PI will be responsible for reporting all SAEs that require reporting to the local or central Institutional Review Board/Ethics Committee (IRB/EC) in accordance with its regulations and guidelines.

16.11. Adverse Event and Serious Adverse Event Follow-up

All AEs and SAEs will be followed up to resolution (the subject's health has returned to her baseline status or all variables have returned to normal) or until an outcome is reached, stabilization occurs (the investigator does not expect any further improvement or worsening of the event) or the event is otherwise explained, regardless of whether the subject is still participating in the study. All appropriate therapeutic measures should be undertaken and recorded. Where appropriate, medical tests and examinations will be performed to document resolution of the event(s).

16.12. Serious Adverse Event Reporting – Procedures for Investigators

Initial Reports and Follow-Up SAE Reports: To report an SAE, the SAE eCRF form within the Electronic Data Capture (EDC) system must be completed. All SAEs, whether or not deemed drug-related or expected, must be reported by the investigator or qualified designee within 24 hours of first becoming aware of the event ([Appendix 3](#)). The investigator/qualified designee will enter the required information regarding the SAE into the appropriate form, which will automatically result in distribution of the information to the appropriate sponsor contact. If the EDC system is temporarily unavailable (>24 hours), the event, including the investigator-determined causality to study drug, should be reported via a paper back-up SAE form to the Safety Surveillance team via (contact information, i.e., e-mail or fax will be available on the SAE form).

Upon return of the availability of EDC system, the SAE information must be entered into the EDC system as soon as possible. The SAE form within the EDC system must be updated within 24 hours of knowledge/receipt of SAE follow-up information.

17. DATA COLLECTION, STUDY MONITORING AND RECORD MANAGEMENT

17.1. Data Collection and Reporting

Data for this study will be collected using eCRFs. The investigator and study site staff will receive training regarding the completion of the eCRF. Visit-specific data should be entered into the eCRF and be ready for review as soon as possible, but no later than 5 days after each visit/time point.

All protocol-required information collected during the study must be entered by the investigator or designated representative in the source documents and eCRF. All data entry, modification or deletion will be recorded indicating the individual subject, original value, the new value, the reason for change, who made the change, and when the change was made. All data changes will be clearly indicated with a means to locate prior values. The investigator will maintain a list of individuals who are authorized to enter or correct data on the eCRFs.

The investigator or designated sub-investigator, following review of the data in the eCRF, will confirm the validity of each subject's data by signing the eCRF.

17.2. Study Monitoring

Study progress will be monitored by the Sponsor or its representative as frequently as necessary to ensure adequate and accurate data collection, protocol compliance, and study conduct in accordance with accepted regulatory requirements. The PI must make all the subject data available to the monitor for review during the planned site monitoring visits. Arrangements for monitoring visits will be made in advance, except in emergency cases.

17.3. Investigator Study Files

The PI is responsible for maintaining all study-related documents in the study files. The Sponsor will notify the PI when retention of study files is no longer necessary. The following documents will be kept in the study files or be readily accessible:

- original protocol and all amendments
- signed agreement or protocol
- signed and dated study staff roles and responsibilities log
- copy of the current *curriculum vitae* of the PI and of all sub-investigators
- IRB/EC membership list and all IRB/EC approvals for the protocol and amendments, informed consent documentation and all updates, advertisements, and written information provided to subjects; all IRB/EC correspondence; documentation that the IB and subsequent revisions have been submitted to the IRB/EC; documentation that all SAEs and any periodic safety reports have been submitted to the IRB/EC; and annual IRB/EC renewals (as required)
- updated laboratory certification and the laboratory's normal values (covering the entire time interval of the study for all laboratory tests conducted during the study)

- all confirmations of investigational drug receipt, drug accountability logs and drug return records
- all correspondence to or from the Sponsor or its designees
- blank informed consent form
- Investigator's Brochure
- subject screening log
- subject list (contains subject initials and/or protocol-specific subject number)
- all subjects' original signed informed consents
- monitoring visit log

17.4. Retention of Records

Essential documents should be retained until at least 2 years after the last approval of a marketing application and until there are no pending or contemplated marketing applications, or at least 2 years have elapsed since the formal discontinuation of the clinical development of the investigational product. These documents should be retained for a longer period, however, if required by the applicable regulatory requirements or by an agreement with the Sponsor.

The Sponsor will inform the PI/institution in writing of the need for record retention and will notify the PI/institution in writing when the trial-related records are no longer needed.

An investigator who withdraws from the responsibility of maintaining study records or wishes to move them to a new location has the obligation to place them in safekeeping and to inform the Sponsor of their location.

18. ANALYTICAL PLAN

All statistical processing will be performed using SAS® version 9.3 or later, unless otherwise stated. All statistical tests will be two-sided and interpreted at a 5% significance level.

The study is not powered for formal statistical comparisons. Descriptive statistics (i.e., mean, standard deviation, median, minimum, maximum, etc.) will be provided for all continuous variables; frequencies and percentages will be tabulated for incidence and categorical variables. For parameters measured over time, observed values and changes from baseline will be described for each time point.

The clinical cure and mycological eradication rates will be described by baseline *Candida* species, when the number of isolates per species allows.

All analyses will be presented by treatment group. Unless otherwise stated, data will be analyzed as is with no imputation. No adjustment for multiplicity will be employed.

A Statistical Analysis Plan (SAP) describing all statistical analyses in detail will be provided as a separate document. The SAP will be finalized prior to database lock.

18.1. Sample Size Determination

The primary efficacy endpoint of the study is the percentage of subjects with clinical cure (complete resolution of signs and symptoms with total composite score of 0 on the VSS Scale with no additional antifungal therapy required based on investigator's judgment) at the TOC visit. This is an exploratory study, and no formal sample size calculation was performed. Approximately 150 subjects will be enrolled in allocation 50:50:50 in respect of 1, 3 or 7 days of treatment. Subjects will be randomized to treatment, stratified by group based on the *Candida* species and presence or absence of underlying medical conditions. A sample size of 150 subjects is estimated to be adequate to perform an initial assessment of efficacy.

18.2. Analysis Populations

The study populations to be used in the analyses are defined as follows:

Intent-to-Treat (ITT) Population: All ibrexafungerp-treated subjects.

Modified Intent-to-Treat (MITT) Population: All treated subjects who have a positive culture for *Candida species* at Screening.

Per-Protocol (PP) Population: All MITT subjects who have completed the study drug treatment, who did not have major protocol deviations likely to affect study efficacy AND who have a TOC evaluation.

Safety Population: All enrolled subjects who received at least one dose of study drug.

18.3. Subject Disposition, Discontinuation, and Baseline Data

Subject disposition in terms of the number and percentage of subjects enrolled by site will be tabulated. The number of subjects enrolled, number completing the study, and reasons for discontinuation will be summarized by treatment group. Subject demographics and baseline characteristics such as age, race, ethnicity, sex, weight, height, body mass index, region (if applicable) and other relevant parameters will be tabulated by treatment group.

Baseline is defined as the last non-missing assessment prior to the date (and time if appropriate) of the first dose of study drug. Change from baseline is defined as: post- baseline value – baseline value.

